Covariates will be identified in data from claims and electronic health records (where available, as not all data research partners will have access to electronic health records) using administrative health plan enrollee data or codes for diagnoses (with procedures or

medications, as appropriate). The following potential variables will be identified in relation to the index date (i.e., cohort entry date), to be included in descriptive analysis and to be considered as potential confounders in analysis of general safety events.

- Demographics (on the index date, unless otherwise noted): age, sex, geographic region (using the latest information available as of the index date), and race/ethnicity (if feasible)
- Date of Pfizer-BioNTech original monovalent COVID-19 Vaccine (categorized as appropriate, e.g., by year or month) and dose of vaccine received (e.g., 1, 2, 3)
- Medical history:
 - Comorbidities (in the 12 months before, not including the index date): history of anaphylaxis, history of allergies, diabetes (type 1, type 2, gestational diabetes in current pregnancy), hypertension, cardiovascular disease, cerebrovascular diseases, chronic respiratory disease, chronic kidney disease, chronic liver disease, cancer, epilepsy, autoimmune disorders, influenza and other respiratory infections (including COVID-19), immunocompromising conditions, gastrointestinal infections, and obesity (capture anticipated to be incomplete)
 - Pregnancy status (on the index date)
 - Medications and non-COVID-19 vaccinations (in the 12 months before or on the index date), including vaccines administered concomitantly with Pfizer-BioNTech original monovalent COVID-19 Vaccine
 - Healthcare utilization (in the 12 months before or on the index date): any healthcare encounter (including telehealth encounters, if feasible); hospitalizations; emergency department visits; cancer screening(s); skilled nursing facility, nursing home, or extended care facility stay; other preventive healthcare services, as appropriate; and COVID-19 tests

For comparative analyses of pregnancy safety outcomes among pregnant women, the following potential confounders and descriptive variables will be identified in relation to the index date.

- Demographics (on the index date, unless otherwise noted): maternal age, geographic region (using the latest available information on index date), race/ethnicity (if feasible)
- Medical history:

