8.3.3. Covariates

Covariates will be identified in claims and electronic health records (where available, as not all data research partners will have access to electronic health records) using administrative health plan enrollee data or codes for diagnoses (with procedures or medications, as appropriate). Detailed algorithms and code lists to identify each covariate will be included in the SAP.

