8.3.3.1. Potential confounding variables

The following variables will be used to describe the overall study population, immunocompromised individuals, individuals with a history of COVID-19, and pregnant women and will be considered as potential confounding variables to be included in propensity score models for analysis of general safety events.

- Demographics will be evaluated at the index date for each individual, unless otherwise noted
- Age: Individuals of all ages will be included in the study; for descriptive analyses, age categories will be 0-4, 5-11, 12-15, 16-20, 21-29, 30-49, 50-64, 65-80, and greater than 80 years
- Sex
- Geographic region (zip code where available, state or census region; evaluated using the latest information available on the index date)
- Race/ethnicity: Data on race/ethnicity are anticipated to be incomplete, and the feasibility of including this variable in the analyses will be assessed before study start
- Date of Pfizer-BioNTech original monovalent COVID-19 Vaccine (categorized as appropriate, e.g., by year or month)
- Dose of vaccine received (e.g., 1, 2, 3)
- Comorbidities, identified in the 12 months before the index date (unless otherwise noted) in claims or electronic health records using diagnosis codes (with procedure and/or pharmacy dispensing codes as appropriate)
 - History of anaphylaxis (not including the index date)
 - History of allergies
 - Diabetes mellitus (type 1, type 2, or gestational diabetes in current pregnancy)
 - Hypertension

PFIZER CONFIDENTIAL

CT24-WI-GL02-RF02 3.0 Non-Interventional Study Protocol Template For Secondary Data Collection Study 20-May-2021 Page 71 of 120

- Cardiovascular disease
- Cerebrovascular disease
- Chronic respiratory disease
- Chronic kidney disease
- Chronic liver disease
- Cancer
- Epilepsy
- Autoimmune disorders
- Influenza and other respiratory infections (including COVID-19)
- Gastrointestinal infections
- Immunocompromising conditions, including the following (to be defined in more detail in the SAP):
 - Immunodeficiencies
 - Immunosuppressant medication use
 - Human immunodeficiency virus and other immunosuppressing conditions
 - Receipt of organ or bone marrow transplant
- Obesity (to be identified with proxies using diagnosis and procedure codes; capture anticipated to be incomplete)
- Preeclampsia/eclampsia (captured only in subgroup analysis of pregnant women)

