- Pregnancy status (on the index date), identified using an algorithm as described in Section 8.2.3
- Medications in the 12 months before and including the index date, identified in data from claims or electronic health records via procedure and/or pharmacy dispensing codes
 - Analgesics

PFIZER CONFIDENTIAL

CT24-WI-GL02-RF02 3.0 Non-Interventional Study Protocol Template For Secondary Data Collection Study 20-May-2021 Page 72 of 120

- Antibiotics
- Antiviral medications
- Corticosteroids
- Nonsteroidal anti-inflammatory drugs
- Psychotropics
- Statins
- Novel oral anticoagulants
- Warfarin
- Non-COVID-19 vaccinations (including those administered concomitantly with Pfizer-BioNTech original monovalent COVID-19 Vaccine) in the 12 months before or on the index date, identified in data from claims or electronic health records with procedure and/or pharmacy dispensing codes
 - Influenza
 - Pneumococcal disease
 - Diphtheria, tetanus, and pertussis
 - Polio
 - Measles, mumps, and rubella
 - Haemophilus influenzae type b
 - Hepatitis B virus
 - Human papillomavirus
 - Meningitis
 - Rotavirus
 - Varicella
 - Herpes zoster

CT24-WI-GL02-RF02 3.0 Non-Interventional Study Protocol Template For Secondary Data Collection Study 20-May-2021 Page 73 of 120

- Healthcare utilization (including telehealth encounters, if feasible) in the 12 months before or on the index date
 - Any healthcare encounter
 - Hospitalizations
 - Emergency department visits
 - Skilled nursing facility, nursing home, or extended care facility stay
 - Cancer screening(s)
 - Other preventive healthcare services, as appropriate
 - COVID-19 tests

The following variables will be used to describe the population of pregnant women and will be considered as potential confounders to be included in propensity score models for analysis of pregnancy safety outcomes. Except where noted, only information up to and including the index date will be used to identify potential confounders.

- Demographics: maternal age (on the index date), geographic region (using the latest information available as of the index date), race/ethnicity (if feasible, on the index date)
- Comorbidities, identified in the 12 months before the index date in claims or electronic health records using diagnosis codes (with procedure and/or pharmacy dispensing codes as appropriate).
 - Diabetes mellitus (type 1, type 2)
 - Hypertension
 - Connective tissue disorders
 - Thyroid disorders
 - Heart disease
 - Epilepsy and mood disorders

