Estimation of propensity scores will be performed for the dose 1, 2, and 3 (if applicable) cohorts combined. However, matching of exposed to unexposed individuals will be done separately for the dose 1 exposed cohort, the dose 2 exposed cohort, and the dose 3 exposed cohort within narrow time periods to account for changing predictors of vaccination over time, seasonality of circulating infections, and changes in healthcare utilization over time. Matching will occur by age and state (if feasible, or broader geographic region if not feasible) within each time period and dose number. The matching and propensity score estimation process will be done first for the general population and then will be repeated separately for immunocompromised individuals and for individuals with a history of COVID-19. Propensity score estimation will be conducted within each data research partner. The steps for propensity score modeling and matching are as follows.

a. Within each data research partner, the study period will be divided into 1-month intervals of calendar time ("time intervals"). All individuals who received a vaccine dose— whether dose 1, dose 2, or dose 3—during the considered month would contribute vaccinated index dates during the time interval; if an individual received more than 1 dose during a calendar month, all eligible index dates will be included as independent observations in the propensity score model. All individuals with at least 1 unexposed

PFIZER CONFIDENTIAL

CT24-WI-GL02-RF02 3.0 Non-Interventional Study Protocol Template For Secondary Data Collection Study 20-May-2021 Page 92 of 120 person-day in the time interval will have an unvaccinated index date randomly assigned during all unexposed person-time within the time interval. In this context, "unexposed person-day" refers to a day in which the individual has no record of COVID-19 vaccine on or before that day.

- b. Within each time interval, the propensity to be vaccinated will be estimated among all individuals with index dates within the time interval using logistic regression. The dependent variable for the logistic regression model will be vaccination status, and the independent variables will be baseline covariates (i.e., individual characteristics as described in Section 8.3.3). The model will combine dose 1, dose 2, and dose 3 index dates, which assumes that the factors influencing an individual's likelihood of being vaccinated does not change between dose 1, dose 2, and dose 3.

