8.7.3.2. Self-controlled risk interval design

Sensitivity analyses incorporating a SCRI design will be implemented for outcomes with an acute onset and short risk intervals (i.e., risk intervals no longer than 42 days; specific outcomes to be indicated in the SAP) in the overall study population, in pregnant women, in immunocompromised individuals, and in individuals with a history of COVID-19. The SCRI design will not be considered for pregnancy safety outcomes. Only vaccinated individuals will be included in the SCRI analysis; the rate of a specific safety event in a post-vaccination risk interval will be compared with that in a control interval within the same individual.

For the primary series analysis, the risk interval will combine person-time in the risk intervals after the first dose, after the second dose, and after the third dose (if applicable).

PFIZER CONFIDENTIAL CT24-WI-GL02-RF02 3.0 Non-Interventional Study Protocol Template For Secondary Data Collection Study 20-May-2021 Page 96 of 120 The control interval will be outcome specific, with the duration and timing relative to vaccination specified in more detail in the SAP. Control intervals will be defined during specific periods following vaccination (up to a maximum of 183 days); to avoid bias due to healthy vaccinee effects, pre-vaccination periods will not be used. A washout period between the risk and control intervals may be incorporated for safety events for which the risk interval is not well characterized.

Because of the self-controlled nature of the design, bias of comparative risk estimates arising from differences in the distribution of time-constant confounding factors between vaccinated and unvaccinated individuals is avoided with the SCRI design. Furthermore, as the design only includes vaccinated individuals, it avoids the potential for misclassification of unexposed status due to incomplete capture of COVID-19 vaccinations in data from claims or electronic health records.

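### The 12-month non-COVID-19 vaccination covariates do not separate a same-day vaccine, and the SCRI does not cover it, so its acute effect can be attributed to the study vaccine

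*Protocol*

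**What the plan says.** Section 8.3.3.1 lists, for general safety events, "Non-COVID-19 vaccinations (including those administered concomitantly with Pfizer-BioNTech original monovalent COVID-19 Vaccine) in the 12 months before or on the index date". The list has twelve vaccine types, from influenza to herpes zoster, with entries such as "Diphtheria, tetanus, and pertussis". The Abstract gives the same window: "Medications and non-COVID-19 vaccinations (in the 12 months before or on the index date), including vaccines administered concomitantly with Pfizer-BioNTech original monovalent COVID-19 Vaccine". These variables "will be considered as potential confounding variables to be included in propensity score models for analysis of general safety events". Section 8.3.3 adds that "Detailed algorithms and code lists to identify each covariate will be included in the SAP".

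In the primary series analysis (Section 8.7.2.3.1.1, step a), each person with unexposed time in a calendar month "will have an unvaccinated index date randomly assigned during all unexposed person-time within the time interval". Table 2 likewise gives third-dose comparators a randomly selected date near the exposed person's dose.

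Table 8 sets risk windows of 42 days or less for every general safety event except narcolepsy and vaccine-associated enhanced respiratory disease.

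Section 8.7.3.2 compares a post-vaccination risk interval with a control interval later in the same person's post-vaccination time. It says that the design avoids "bias of comparative risk estimates arising from differences in the distribution of time-constant confounding factors". The sensitivity analyses in Section 8.7.3 and the limitations in Section 8.9 do not mention co-administration.

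**The concern.** An exposed person who receives another vaccine at the same visit is on day 0 of that vaccine's own acute period when follow-up starts. A comparator matched on having had the same vaccine type within 12 months may have had it at any time in that year. The two are balanced on the covariate but not on acute risk.

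The SCRI is offered in Section 8.9 as the check on confounding, and Sections 8.1, 8.3.1 and 8.9 allow it to become the primary design. It shares this weakness: a vaccine given on day 0 acts in the same risk interval as the study dose, and its acute effect is over by the control interval. On this one point, agreement between the two designs would not be independent reassurance.

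The protocol already recognises the asymmetry elsewhere. The Version 4.0 amendment took the index date out of the comorbidity look-back because exposed people are likelier than comparators to have a healthcare encounter that day. The vaccination look-back still includes it.

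At stake is the reading of modestly raised RRs for acute outcomes. Primary objective 2 covers children aged 6 months through 4 years, and the covariate list includes routine childhood vaccines.

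**Working it through.** **Plan figure for scale.** The protocol has no figure on co-administration. The nearest is the Section 8.5 example (myocarditis/pericarditis, 5,000,000 vaccinees, 2 doses each, 10 per 100,000 person-years, 21 days, true RR 1.4, 1:1).
- Expected comparator events: E0 = 5,000,000 × 2 × (21/365.25) × 0.0001 = 57.5. Exposed: E1 = 1.4 × 57.5 = 80.5.
- SE(log RR) = √(1/57.5 + 1/80.5) = 0.173.
- P(upper limit < 2.5) = Φ[(ln(2.5/1.4) − 1.96 × 0.173)/0.173] = 0.919, which agrees with the stated 92%.

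The point below does not depend on this figure. It shows that Table 9 works with true RRs of 1.0, 1.2 and 1.4.

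**Inputs, all assumed because the protocol gives none.**
- p: share of study doses with another vaccine on the same day, 0.10 to 0.20.
- r: acute RR of that vaccine for the outcome, averaged over the window, 2 to 3.
- q: 12-month prevalence of that vaccine type, made equal in both groups by matching, 0.3 to 0.7.
- Window W = 42 days; true study-vaccine RR = 1; vaccinations not on the index day spread evenly over the year.

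**SCRI.** Apparent RR = 1 + p(r − 1), if no other vaccine acts in the control interval.

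**Cohort.**
- Share of comparator follow-up inside the other vaccine's window: f = q × 21/365 (21 = W/2).
- Same share in the exposed: fe = p + (q − p) × 21/365.
- Apparent RR = [1 + fe(r − 1)]/[1 + f(r − 1)].

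Example with p = 0.10, r = 3, q = 0.5: f = 0.0288; fe = 0.10 + 0.40 × 0.0575 = 0.1230; RR = 1.2460/1.0575 = 1.178. The SCRI gives 1 + 0.10 × 2 = 1.20.

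| p | r | SCRI | Cohort, q = 0.7 to 0.3 |
|---|---|---|---|
| 0.10 | 2 | 1.10 | 1.091 to 1.093 |
| 0.10 | 3 | 1.20 | 1.174 to 1.182 |
| 0.20 | 2 | 1.20 | 1.181 to 1.185 |
| 0.20 | 3 | 1.40 | 1.349 to 1.364 |
| 0 | any | 1.00 | 1.00 |
| any | 1 | 1.00 | 1.00 |

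Exact balance on the 12-month variable removes little. On the log scale the cohort keeps between ln 1.174/ln 1.20 = 0.88 and ln 1.185/ln 1.20 = 0.93 of the SCRI bias.

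**Two checks on the cohort formula (p = 0.10, r = 3, q = 0.5).**
- Shorter window, W = 21: f = 0.5 × 10.5/365 = 0.0144; fe = 0.10 + 0.40 × 10.5/365 = 0.1115; RR = 1.2230/1.0288 = 1.19, closer to the SCRI value.
- Seasonal clustering, with the earlier-vaccine terms tripled (assumed): f = 0.0863; fe = 0.10 + 0.0690 = 0.1690; RR = 1.3381/1.1726 = 1.14. Clustering reduces the bias but does not remove it.

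**The case against.** The strongest case against is that the protocol gives a look-back window, not a coding rule. It names concomitant doses expressly and leaves algorithms, score specification and SCRI detail to an SAP that is not at hand, which could add a same-day indicator. It nowhere claims that either design isolates co-administered vaccines: Section 8.7.3.2 speaks of time-constant confounders only, and Section 8.9 concedes residual confounding in the cohort. Both inputs to the size of the bias come from outside the documents.

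Much of this stands, and it rules out stronger readings that a reader might infer:
- That the covariate is a single flag for any other vaccination. It is not; twelve types are listed.
- That a co-administered vaccine's risk is in fact credited to the study vaccine. The protocol shows only that it can be; this needs an acute effect of that vaccine on that outcome and a non-trivial share of doses.
- That the SCRI is fully confounded. Doses given alone inform the contrast, and routine doses falling in the control interval would reduce the bias.
- That the SCRI expression applies unchanged to the cohort. It slightly overstates the bias there.

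Deferral to the SAP does not dispose of the point. The protocol itself fixes the window and the inclusion of same-day doses. A same-day indicator added to the propensity score would seldom be present among comparators indexed on random days, so overlap would be poor. Restriction or stratification is a design choice, and none is named in Sections 8.7.3 or 8.9.

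**Conclusion.** The point holds in limited form. The type-specific 12-month covariates do not separate a same-day vaccine from an earlier one, balancing on them does not equalise acute risk, and the SCRI as described does not address the gap.

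Under the assumed 10-20% share and co-vaccine RR of 2-3, the upper end of the bias is as large as the true RRs of 1.2 and 1.4 used in Table 9. These sizes are illustrations, not estimates. The bias is proportional to the co-administration share in the SCRI and nearly so in the cohort, and it confines itself to outcomes that the other vaccine affects. Nothing in the protocol shows that such an effect exists for any listed outcome, so the point does not establish that any planned estimate will be wrong. It is a gap that is cheap to close and worth closing.

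**What to change.** For general safety events with risk windows of 42 days or less:
1. Define same-day vaccination separately from earlier vaccination, by type, so that the 12-month covariate no longer merges the two.
2. Add a sensitivity analysis in both the cohort and the SCRI, restricted to index dates with no non-COVID-19 vaccine on the same day or within the preceding risk window for that outcome. In the cohort, apply the restriction to exposed and comparators alike.
3. Report co-administered doses as a separate stratum, with their number and share, and label that estimate as the joint effect of the vaccines given together.

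The main analysis can stay as planned. The vaccination codes are already being captured, so the cost is extra analysis runs and wider intervals in the restricted analysis, widest where co-administration is common. Reporting the share would also replace the assumed p with an observed one.

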4. AMENDMENTS AND UPDATES

PFIZER CONFIDENTIAL

CT24-WI-GL02-RF02 3.0 Non-Interventional Study Protocol Template For Secondary Data Collection Study 20-May-2021 Page 25 of 120

Amendment number	Date	Protocol section(s) changed		Summary of amendment(s)	Reason
Version 4.0		Abstract, Section 6	•	Revised background to describe regulatory updates for Pfizer- BioNTech original monovalent COVID-19 Vaccine, including that the original monovalent vaccine is no longer authorized as of 18 April2023	To accommodate new emergency use authorizations of the Pfizer-BioNTech COVID-19 Vaccine since Version 3.0 of the protocol
Version 4.0		Abstract, Section 8.1	•	Added end date (18 April 2023) for exposure assessment window	To align with date original monovalent vaccine was no longer authorized
Version 4.0		Abstract, Section 8.1, Section 8.2.2, Section 8.7.2	•	Added "sex" as matching criterion for comparative analysis of general safety outcomes	To include matching variable inadvertently omitted previously
Version 4.0		Abstract, Section 8.2.2	•	Clarified eligibility criteria for individuals older than 1 year of age versus children 12 months or younger	To accommodate reduced enrollment criteria (birth to index date) in children 12 months or younger
Version 4.0		Abstract, Section 8.2.3, Table 3, Section 8.7.2	•	Added language to clarify outcomes of major congenital malformations and small size for gestational age will be assessed only in singleton pregnancies	To minimize impact of confounding by multiple pregnancy on these birth outcomes
Version 4.0		Abstract, Section 8.3.3	•	Changed comorbidity assessment period to 12 months before the index date, not including the index date	To exclude assessment of relevant comorbidities on the date, as exposed individuals are more likely to have an outpatient or inpatient healthcare encounter on the index date relative to comparators, which could lead to imbalance in the 2 groups
Version 4.0		Abstract, Section 8.3.3	•	Added preeclampsia/eclampsia and gestational hypertension as covariate potential confounding variables	To allow for additional potential confounding variables among pregnant

PFIZER CONFIDENTIAL

CT24-WI-GL02-RF02 3.0 Non-Interventional Study Protocol Template For Secondary Data Collection Study 20-May-2021 Page 26 of 120

Amendment number	Date	Protocol section(s) changed		Summary of amendment(s)	Reason

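### The healthcare-utilization covariate counts the index date, which is the vaccination visit for the exposed and a random day for comparators, so the propensity score can be set partly by the vaccination itself

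*Protocol*

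**What the plan says.** Section 8.3.3.1 gives one list of variables that describes the populations and supplies candidates for the score. The listed variables "will be considered as potential confounding variables to be included in propensity score models for analysis of general safety events". The list includes "Healthcare utilization (including telehealth encounters, if feasible) in the 12 months before or on the index date", with any encounter and other preventive services among its components. The abstract repeats the window: "Healthcare utilization (in the 12 months before or on the index date): any healthcare encounter (including telehealth encounters, if feasible". The medication window also takes in the index date: "Medications in the 12 months before and including the index date". The same list carries vaccine date and dose number: "Date of Pfizer-BioNTech original monovalent COVID-19 Vaccine (categorized as appropriate, e.g., by year or month" and "Dose of vaccine received (e.g., 1, 2, 3".

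Section 8.7.2.3.1.1, step b, regresses vaccination status on the Section 8.3.3 characteristics within 1-month intervals, pooling doses 1 to 3, and excepts none of these items. Table 1 sets the exposed index date at the date of the dose. Step a assigns the unvaccinated index date at random within the person's unexposed time in the month.

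Version 4.0 excluded the index date from the comorbidity window. The reason given in Section 4 is that "exposed individuals are more likely to have an outpatient or inpatient healthcare encounter on the index date relative to comparators", which could unbalance the groups.

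**The concern.** Day 0 is a healthcare contact by design in one group and an ordinary day in the other. A covariate that counts encounters on day 0 is therefore partly a consequence of exposure. The sponsor's reason for the comorbidity change is about encounters, yet the variable that counts encounters kept day 0, and no reason is given for the difference.

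A vaccinee with no care in the previous year can be recorded as a care user and matched to a comparator who really used care. Prior healthcare use predicts both vaccination and whether an event gets recorded, so it is a covariate the score needs to get right. Section 8.7.1 checks balance by standardized differences on the same recorded covariates, so the check would not show the problem. If people without prior care have fewer recorded events, the distortion pushes the RR down, which is the unfavorable direction for a safety study.

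**Working it through.** **1. Does the text produce the mechanism?**

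- Exposed index date: the dose date (Section 8.2.2.1, Table 1).
- Comparator index date: a random day in the month (Section 8.7.2.3.1.1, step a).
- Utilization window: closes on the index date (Section 8.3.3.1 and abstract).
- Model inputs: the Section 8.3.3 characteristics (step b).
- Data model: procedure records, with date of vaccination as the protocol's example, carry an encounter identifier and encounter type (Section 8.4). A procedure-coded dose can therefore supply an encounter. Doses are also identified from pharmacy dispensings (Section 8.3.1), which Section 8.4 lists separately from encounters and which may supply none.

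So the mechanism follows from the text, but its frequency does not.

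**2. The protocol's own figure.** Section 8.5 gives a 92% probability that the upper limit is below 2.5 (5,000,000 vaccinated, 10 per 100,000 person-years, RR 1.4). With 2 doses and a 21-day window, person-years = 5,000,000 × 2 × 21/365.25 = 574,949. Expected events are 57.5 and 80.5, and SE = √(1/57.5 + 1/80.5) = 0.173. Then Φ((ln 2.5 − ln 1.4)/0.173 − 1.96) = 0.919, which reproduces the figure. It does not use the propensity score and is unaffected by this point.

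**3. Illustrative size.** All inputs here are assumptions. Let f be the share of vaccinees with no encounter in the prior 12 months, let their recorded event rate be half that of users, and let p be the share of vaccinations that create an encounter record. Matching is on the encounter flag alone, index-day encounters in comparators are ignored, and the true RR is 1.

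- Vaccinees still recorded as non-users: f(1 − p). The matched comparators have this share of true non-users.
- Relative event rate in vaccinees: 1 − 0.5f. In matched comparators: 1 − 0.5f(1 − p).
- Apparent RR = (1 − 0.5f) / (1 − 0.5f(1 − p)).

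For f = 0.15 the numerator is 0.925. The denominators are 0.94 (p = 0.2), 0.9625 (p = 0.5) and 1 (p = 1).

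| f | p = 0.2 | p = 0.5 | p = 1 |
|---|---|---|---|
| 0.10 | 0.990 | 0.974 | 0.950 |
| 0.15 | 0.984 | 0.961 | 0.925 |
| 0.25 | 0.972 | 0.933 | 0.875 |

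**4. Check by simulation** (200,000 people, assumed inputs). A latent care-seeking trait drives both a prior-year encounter and vaccination. The score uses one binary encounter flag, and comparators are weighted to the exposed. Index-day encounters occur in 3% of comparators. With day 0 excluded, the encounter–vaccination odds ratio is 2.02 and the standardized difference in the true prior encounter is 0.00. With day 0 included:

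| Exposed with an index-day encounter | Odds ratio | Standardized difference, true prior encounter |
|---|---|---|
| 5% | 2.05 | 0.01 |
| 20% | 2.52 | −0.07 |
| 50% | 4.33 | −0.23 |
| 90% | 22.8 | −0.49 |

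A negative sign means the weighted comparators used more prior care than the vaccinees. In the same runs the latent trait, which the flag measures only in part, was 0.27 SD higher in vaccinees with day 0 excluded and 0.17 SD higher in the 90% case. The distortion can thus partly offset other residual confounding by accident, so step 3 isolates one component and does not predict the net bias.

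**The case against.** **The list is provisional.** Its items are only to be considered for the score, it also serves description, and the SAP may narrow it. This stands for vaccine date and dose. It does not remove the main point: the protocol itself states the utilization window, step b takes in Section 8.3.3 without exception, and Section 8.3.3 leaves covariate algorithms and code lists to the SAP, not the window.

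**Many vaccinations may leave no encounter record.** This stands. Pharmacy-dispensed doses may not, and p cannot be derived from the protocol. Other covariates, such as comorbidities and screening, would also tend to pair low-care vaccinees with low-care comparators.

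**Safeguards exist.** Overlap plots precede matching, and the self-controlled analysis (Section 8.7.3.2) does not use the score. But a plot of scores built on the affected covariate does not reveal the error, and the self-controlled design is a sensitivity analysis for selected outcomes. Neither repairs the primary cohort estimate.

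**Dropping day 0 is not enough for doses 2 and 3.** This stands. Their look-back typically contains an earlier vaccination visit, so the fix has to be wider.

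Three stronger readings are tempting, and the protocol does not support them. A reader might infer that the visit also creates the medication and COVID-19 test covariates, but the listed classes are ordinary drugs such as statins and antibiotics, and a vaccination is not a test. A reader might infer that vaccine date and dose separate the groups perfectly, but date by month or year is nearly constant within a 1-month model, and dose number does not fit a model that pools the doses and assumes common predictors. A reader might infer that unvaccinated non-users are never matched, but that requires practically every vaccination to create an encounter record.

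**Conclusion.** The point holds for healthcare utilization. As written, the window lets the vaccination contact set the encounter covariate, and possibly the preventive-services one, and the protocol's own amendment rationale applies directly. The third-dose analysis (Section 8.7.2.3.1.2) follows similar scoring steps and inherits the problem.

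The size is uncertain. With 15% prior non-users at half the recorded event rate, a null RR of 0.98 to 0.96 goes with 20% to 50% of vaccinations creating an encounter. The value 0.93 is the limit at 100% and should not be read as a central estimate. If index-day encounters are about as common in both groups (5% against 3% in the simulation), nothing material happens. Medications are at most a matter of consistency, and vaccine date and dose a matter of labelling. The change is worth making because the error is avoidable, would not show in the balance table, and costs almost nothing to remove.

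**What to change.** In Section 8.3.3.1 and the abstract, for the propensity models:

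- End the healthcare-utilization look-back on the day before the index date, as already done for comorbidities.
- Do not count COVID-19 vaccination encounters as utilization at any point in the look-back, so that earlier doses do not enter the dose 2 and dose 3 scores.
- Optionally, for consistency, end the medication window on the day before the index date too.
- Mark vaccine dose and vaccine date as descriptive only. Dose is undefined for never-vaccinated comparators, and the 1-month intervals already handle calendar time.

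The window for other vaccines need not change for this point, since the protocol deliberately records co-administered vaccines. The cost is a wording change, one day of look-back and a rule for recognizing vaccination encounters. The study-size figures stay as they are.
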